1.0 Objectives

1.1 Objective: The objective of this study is to obtain preliminary information regarding how a menthol ban that either exempts or includes e-cigarettes is likely to affect overall tobacco use

1.2 Specific Aims: The following specific aims will be pursued:

Aim 1: Determine the impact of the availability of menthol flavor in e-cigarettes on overall tobacco product use patterns

We hypothesize that menthol cigarette smokers will smoke fewer cigarettes, vape more e-cigarettes, have higher motivation to quit smoking and be more supportive of a ban on menthol cigarettes when given the option of using menthol flavored e-cigarettes than when no such option is present.

Aim 2: Determine if the impact of the availability of menthol flavor in e-cigarettes on tobacco use behavior is moderated by a ban on menthol flavor in cigarettes

We hypothesize that the impact of menthol flavored e-cigarette availability on the above measures will be greater during a simulated ban on menthol cigarettes than if smokers can continue smoking menthol cigarettes.

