3.0 Study Endpoints/Events/Outcomes

3.1 Primary Endpoint/Event/Outcome: The primary outcome is the amount of each tobacco product used per week as recorded on their tobacco use surveys.

3.2 Secondary Endpoint(s)/Event(s)/Outcome(s): Secondary outcomes measured at each visit include how much of each product is obtained from the experimental marketplace, motivation and self-efficacy to quit smoking cigarettes and to quit all tobacco product use, number of quit attempts, severity of craving and withdrawal symptoms, and exhaled carbon monoxide concentrations. Support for a menthol ban and urinary cotinine concentrations will be assessed at baseline and at week 6.

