4.0 Study Intervention(s)/Investigational Agent(s)

4.1 Description: Subjects will be randomized to one of three experimental marketplaces (20 subjects in each condition): 1) a condition simulating a ban on menthol cigarettes but not menthol e-cigarettes (condition A); 2) a condition simulating a ban on both menthol cigarettes and menthol e-cigarettes (Condition B); and 3) a condition in which menthol is not banned for either product (Condition C – the control condition). All conditions would have medicinal nicotine available if subjects decide to quit tobacco products entirely.

The goal of the experimental marketplace is to provide a context in which product preferences can be evaluated in a systematic way but with a high degree of ecological validity. We have therefore included in the marketplace both a

cigarette-like e-cigarette system and a tank-like e-cigarette system (which has the potential to deliver higher doses of nicotine), as those are the two most commonly used e-cigarette systems currently available.

Products available to subjects in each experimental marketplace		
Condition A (menthol ban for cigs)	Condition B (menthol ban for cigs and e-cigs)	Condition C (no menthol ban)
- Non-menthol cigarettes	- Non-menthol cigarettes	- Menthol & non-menthol cigarettes
- Menthol & tobacco flavored versions of commonly used cigarette-like e-cigarette (e.g., Vuse)	- Tobacco flavored version of commonly used cigarette-like e-cigarette (e.g., Vuse)	- Menthol & tobacco flavored versions of commonly used cigarette-like e-cigarette (e.g., Vuse)
- Menthol & tobacco flavored versions of commonly used tank-like e-cigarette (e.g., Joyetech eGo AIO)	- Tobacco flavored version of commonly used tank-like e-cigarette (e.g., Joyetech eGo AIO)	- Menthol & tobacco flavored versions of commonly used tank-like e-cigarette (e.g., Joyetech eGo AIO)
- Nicotine gum and lozenge (various flavors)	- Nicotine gum and lozenge (various flavors)	- Nicotine gum and lozenge (various flavors)

We will include the subject's usual brand of cigarettes in the marketplace (either the non-menthol version or both the non-menthol and menthol version depending on the randomization). Information about their usual brand will be collected at the screening visit in order to incorporate it into the marketplace.

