5.2.3 Evaluation Visits (3 visits occurring at 2 week intervals). Subsequent to the baseline visit, subjects will be evaluated at 3 visits occurring at two week intervals (i.e., at approximately 2, 4 and 6 weeks after the baseline visit). To each visit, subjects will be asked to bring back any unused product as well as all used and unused e-cigarette cartridges or e-fluid vials. The cartridges and vials will be weighed prior to distribution and after use to determine the extent to which they were used. Participants will be allowed to keep any of the unused products so as to not discourage them from bringing back unused product.

At each visit, exhaled carbon monoxide concentrations will be measured and subjects will complete questionnaires assessing various aspects of smoking behavior including craving, withdrawal symptoms and motivation to quit smoking. Questionnaires assessing how they rate the effects of the products they are using and their perceived health risks of using these products will also be assessed. A food diary asking primarily about dietary menthol will be completed to determine if dietary intake changes occur if menthol in tobacco products is no longer available. Level of support for a ban on a variety of menthol containing tobacco products will be evaluated at the baseline and week 6 visits.

Additionally, at the week 6 visit urine will be collected in order to measure cotinine concentrations. At each visit (except for the week 6 visit), subjects will again have the opportunity to obtain additional products for the subsequent 2 weeks using their available credits. They may choose to obtain any of the available products in their marketplace and are not limited to products that they had previously chosen.

5.3 Individually Identifiable Health Information: All information is collected directly from subjects (i.e., medical records will not be requested) and this is not a treatment study. The data being collected therefore does not meet the definition of PHI.

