16.0 Data Management

16.1 Data Analysis Plan: Means (arithmetic or geometric for log-transformed variables) and their corresponding confidence intervals will be calculated for each study condition. Results will also be tabulated separately for men and women. A linear mixed model will be fit for each outcome variable, with fixed categorical effects of group, time, and their interaction, and random subject effects to account for correlation among repeated measurements on the same subject. We expect randomization to balance groups with respect to important baseline covariates such as cigarettes smoked per day and degree of nicotine dependence; however, we will check this assumption using ANOVA and consider adjustment for imbalanced factors. Exploratory modeling of gender and race / ethnicity effects will also be performed. Model contrasts will be used to evaluate the hypotheses of the two aims, primarily that cigarettes smoked will be lower and e-cigarette use higher when menthol e-cigarettes are available (Aim 1: conditions A and C compared to B), and that these effects will be larger when menthol cigarettes are unavailable (Aim 2: condition A compared to C)

16.2 Power Analysis: The main purpose of this project is to provide initial information regarding how banning menthol in either only cigarettes or in both cigarette and e-cigarettes will influence tobacco use patterns so as to better design a subsequent study that more definitively addresses this issue. This study will also provide feasibility information regarding using an experimental marketplace for assessing this question. For this pilot study, we plan on recruiting 60 subjects and anticipate (assuming 10% dropout), that there would be 18 evaluable subjects per group. If there is a large effect, we should be able to detect it as this sample size will provide 80% power for a between-groups time-averaged effect size of 0.8, assuming two-sided alpha=0.05 and within-subject autocorrelation of 0.6.

16.3 Data Integrity: In order to ensure that data entry is correct, data collected on paper questionnaires will be entered twice with the two entries compared and any discrepancies resolved.

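### Aim 2 asks about moderation, but the three arms cannot estimate it: A versus C is the cigarette-ban effect plus the interaction, and the two cannot be separated

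*Combined protocol and SAP*

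**What the plan says.** Section 1.2, Aim 2, asks whether the impact of menthol e-cigarette availability on "tobacco use behavior is moderated by a ban on menthol flavor in cigarettes". Its hypothesis is that this impact will be "greater during a simulated ban on menthol cigarettes than if smokers can continue smoking menthol cigarettes".

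Section 4.1 defines three arms of 20. Condition A is "a condition simulating a ban on menthol cigarettes but not menthol e-cigarettes (condition A"). Condition B bans menthol in both products. Condition C, the control, is "a condition in which menthol is not banned for either product". The product table in 4.1 confirms that A and C both stock menthol e-cigarettes and B does not.

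Section 16.1 fits a linear mixed model with group, time and their interaction, and uses contrasts for the aims. Aim 1 compares A and C with B. For Aim 2 the claim is "that these effects will be larger when menthol cigarettes are unavailable (Aim 2: condition A compared to C").

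Section 16.2 gives the sample-size basis: 18 evaluable per group and "80% power for a between-groups time-averaged effect size of 0.8, assuming two-sided alpha=0.05 and within-subject autocorrelation of 0.6".

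**The concern.** Moderation compares two effects. Here it is the effect of menthol e-cigarette availability under the ban minus the same effect without the ban. The second effect needs an arm with menthol cigarettes but no menthol e-cigarettes, and there is none. In the contrast assigned to Aim 2, availability does not vary at all; what varies is the cigarette ban.

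If the ban itself changes tobacco use, A versus C can be significant when there is no moderation, or can miss moderation that exists. More participants in these arms would not help, because the problem is identification rather than precision. One of the two stated aims would then get a conclusion that its test cannot support in either direction. Since 16.2 says the pilot exists to help design a later study, a ban effect misread as moderation could be carried into that design.

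**Working it through.** **1. Layout (4.1).** Cross the cigarette ban with menthol e-cigarette availability:

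| | Menthol e-cigarettes available | Not available |
|---|---|---|
| Menthol cigarettes banned | A | B |
| Menthol cigarettes allowed | C | D (no such arm) |

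**2. Algebra.** Write each cell mean as μ + b·(ban) + e·(menthol e-cigarettes) + g·(both). Here b is the ban effect without menthol e-cigarettes (B − D), and g is the moderation.

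- Aim 2 as worded: (A − B) − (C − D) = g.
- Planned contrast: A − C = b + g.

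Three arm means cannot determine four parameters. The three-arm design matrix has rank 3, and adding the row for g raises it to 4, so g is not estimable. A − C equals g only if b = 0.

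**3. Reproducing the plan's power.** Inputs are 18 per arm, correlation 0.6 and two-sided alpha 0.05 (16.2), with m = 3 measurements inferred from "Evaluation Visits (3 visits occurring at 2 week intervals") in 5.2.3.

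- SE in SD units = √[(2/18)(1 + (m − 1)·0.6)/m] = √[(2/18)(2.2/3)] = 0.2854.
- Power at 0.8 = Φ(0.8/0.2854 − 1.96) = Φ(0.843) = 80.0%, which matches 16.2.

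The primary outcome is weekly ("The primary outcome is the amount of each tobacco product used per week as recorded on their tobacco use surveys"), so six weekly values are an alternative: m = 6 gives SE = √[(2/18)(4/6)] = 0.2722.

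**4. False moderation (g = 0).** P(significant) = Φ(|b|/SE − 1.96) + Φ(−|b|/SE − 1.96). The ban effects are assumed.

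| Ban effect (SD) | m = 3 | m = 6 |
|---|---|---|
| 0 | 5.0% | 5.0% |
| 0.2 | 10.8% | 11.4% |
| 0.4 | 28.9% | 31.2% |
| 0.8 | 80.0% | 83.6% |

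A t test with 34 df at m = 3 gives 27.5% at 0.4 SD and 77.7% at 0.8 SD, so the normal approximation matters little.

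**5. On the cigarette scale.** The pilot in 2.2.1 reports 11.9 falling to 9.8 cigarettes/day, a change of 2.1, with no SD. If b were 2.1 and g = 0, the chance of significance in the hypothesized direction (nominally 2.5%), at m = 3, is:

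| Assumed SD (cigarettes/day) | Ban effect (SD) | Chance |
|---|---|---|
| 4 | 2.1/4 = 0.525 | 45% |
| 6 | 2.1/6 = 0.35 | 23% |
| 8 | 2.1/8 = 0.263 | 15% |

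For 2.1 to equal 0.8 SD, the SD would have to be 2.1/0.8 = 2.6.

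**6. Masking (interaction of −0.8 SD, m = 3).**

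- Ban effect 0: detected 80%.
- Ban effect +0.4 SD: net −0.4, detected 29%.
- Ban effect +0.8 SD: net 0, detected 5%.

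**7. What a test of moderation would need.** With arm D added, g = A − B − C + D is estimable, with SE √[(4/n)(2.2/3)]. At n = 18 per arm the SE is 0.4037, and power for a 0.8 SD interaction is Φ(0.8/0.4037 − 1.96) = 51%. For 80% power, n = 4(2.2/3)[(1.960 + 0.842)/0.8]² = 35.97, so 36 per arm: 144 evaluable, or 144/0.9 = 160 randomized at the plan's 10% dropout.

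**The case against.** **It is a pilot, and the main objective survives.** This stands in part. Section 1.1 asks how bans that exempt or include e-cigarettes affect tobacco use, and randomized comparisons of A, B and C answer that. A versus C is a valid estimate of the ban effect with menthol e-cigarettes on offer; only the label is wrong. But the label is the conclusion of a stated aim.

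**Baseline could stand in for the missing arm.** Entrants buy only menthol cigarettes and do not regularly use other tobacco, daily surveys start before the marketplace, and the model includes time. One could therefore read the effects in 16.1 as change from baseline. This does not rescue the test. Baseline precedes the credits, the discounted prices and the supplied e-cigarettes, so time and marketplace entry are mixed in, and the change in A still contains the ban effect. Section 16.1 specifies no such contrast.

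**The magnitudes are illustrative.** This stands. No section measures the ban effect inside the marketplace. The 2.1 cigarettes/day comes from an uncontrolled before-after study without a marketplace and with no e-cigarette outcome reported; it makes a ban effect plausible without sizing it. For cigarettes, the masking case needs a ban that raises smoking, against the direction of that pilot, so false moderation is the better-supported risk for that outcome.

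**Neighbouring text has related problems.** This also stands. The end of 2.3 repeats the moderation framing. By the same algebra, the Aim 1 contrast is (A + C)/2 − B = e + g/2 − b/2, so it carries minus half the ban effect. Only A versus B isolates menthol e-cigarette availability, and only under the ban. Neither point weakens the Aim 2 finding.

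**Conclusion.** The concern holds, and Aim 2 is wrong as written. Without a further assumption, moderation is not estimable from these three arms, and the documents state no such assumption. That conclusion rests on the arm definitions alone.

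The practical size depends on the unknown ban effect. Under the protocol's inputs with three measurements, the chance of a significant A versus C with no moderation runs from 5% to 80% as the assumed ban effect goes from 0 to 0.8 SD. Detection of a true 0.8 SD interaction can fall from 80% to 29% or 5% when the ban effect opposes it by 0.4 or 0.8 SD. The 80% power in 16.2 is for a simple two-group difference, not for an interaction.

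**What to change.** - **1.2:** restate Aim 2 and its hypothesis as the effect of banning menthol cigarettes when menthol e-cigarettes remain available. Remove the moderation wording and the claim that the availability effect is greater under a ban.
- **16.1:** reword the Aim 2 hypothesis so that it predicts less smoking and more e-cigarette use under a menthol-cigarette ban with menthol e-cigarettes still on offer, tested by A versus C. If the sponsor does not wish to commit to that direction, it is enough to label A versus C as this ban effect.
- **Add one sentence:** moderation needs a condition with menthol cigarettes but without menthol e-cigarettes, and is left to the subsequent study.
- **2.3:** bring the closing sentence into line.
- **Optional:** report B versus C as the effect of a ban on both products.

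Arms, data collection, model and the A versus C contrast do not change. The cost is giving up a moderation claim in one of two stated aims, and changing that aim's wording in a project already submitted for funding (24.0). Keeping the moderation aim would need the fourth arm and, for 80% power at 0.8 SD, about 160 randomized instead of 60.

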17.0 Confidentiality

17.1 Data Security: To ensure confidentiality, all subjects will be assigned a study identification code to be used on all data collection forms except those for which use of personal identifiers is mandatory (e.g., informed consent form). Forms that link the name of the participant and the subject identification code will be kept in a locked cabinet or office or in an electronic file stored on servers maintained by the University of Minnesota Academic Health Center. Visits will be conducted at the CTSI, therefore there will be a record of the subject's

participation in the CTSI records although a copy of the consent form will not be placed in the participants' medical records.

18.0 Provisions to Monitor the Data to Ensure the Safety of Participants

If the IRB determines this subject to involve Minimal Risk then no independent monitoring will be needed (per IRB guidelines). In this study we will be providing commercially available tobacco products and commercially available over the counter nicotine gum and lozenges to smokers who are not interested in quitting smoking. All products will be provided with the labelling that normally accompanies it. The risks are therefore no greater than if subjects were to purchase these products outside of the study.

If the IRB determines this study to involve more than Minimal Risk, the CTSI monitoring group will be asked to monitor this study using their standard procedures.

The PI will meet regularly with research staff (at least bi-weekly) throughout the project. During these meetings, the study team will evaluate the progress of the trial, review data quality, recruitment, retention, and examine other factors that may affect study outcomes. They will also review adverse events to determine if there are any changes in participant risk. Additional meetings will occur if concerns regarding a particular participant or another problem should arise.

19.0 Provisions to Protect the Privacy Interests of Participants

19.1 Protecting Privacy: During the consent process, subjects will be told that they can discontinue participation at any time for any reason. Furthermore, they are free to not answer any questions asked on the questionnaires. However since certain information is needed to assess eligibility or to assess measures of interest, declining to answer certain questions may lead to a subject not being eligible to participate or to continue with the study.

20.0 Compensation for Research-Related Injury

20.1 Compensation for Research-Related Injury: No compensation is available in the event of research related injury.

21.0 Consent Process

21.1 Consent Process (when consent will be obtained): Informed consent will be obtained at the screening visit. Subjects will have the opportunity to read the consent document and ask any questions that they have. A member of the study staff will then ask the subject questions to make sure that they understand the

study procedures. No study procedures will be administered until the subject has signed the consent form.

21.2 Waiver or Alteration of Consent Process (when consent will not be obtained): N/A

21.3 Non-English Speaking Participants: N/A

21.4 Participants Who Are Not Yet Adults (infants, children, teenagers under 18 years of age): Individuals under the age of 18 will be excluded from the study. Subjects will be asked to present ID at the screening visit to confirm that they are at least 18 years of age.

21.5 Cognitively Impaired Adults or Adults with Fluctuating or Diminished Capacity to Consent: We are not planning on enrolling subjects with fluctuating or diminished capacity to consent. Subjects that appear to have impaired capacity to consent during the consent process will be excluded from the study.

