4.3 IND/IDE. N/A

4.4 Biosafety: N/A

5.0 Procedures Involved

5.1 Study Design: This is a pilot study in which over a 6 week period, menthol cigarette smokers will receive all of their tobacco products from a simulated experimental marketplace. Smokers will be assigned to one of three marketplace conditions: 1) a condition simulating a ban on menthol cigarettes but not menthol e-cigarettes; 2) a condition simulating a ban on both menthol cigarettes and menthol e-cigarettes; and 3) a condition in which menthol is not banned for either product (i.e., the control condition). All conditions would have medicinal nicotine available if subjects decide to quit tobacco products entirely. Subjects would receive "credits" that they can exchange, at visits occurring every two weeks, for any product available in their randomized marketplace condition. At the end of the experimental period any unused credits can be exchanged for monetary payment.

5.2 Study Procedures: The following procedures will occur during the study.

5.2.1 Screening Visit: Initial eligibility will be assessed via a phone interview or online screening form housed on REDCap. All screened participants will be notified by phone or email regarding their eligibility to be scheduled for a screening visit at which written informed consent will be obtained and eligibility

confirmed. At the screening visit, medical and psychiatric history will be obtained via subject report. Women will have a urine pregnancy test to confirm that they are not pregnant. A medical professional (e.g., Nurse Practitioner) will review medical histories to ensure eligibility. Baseline questionnaires assessing smoking history will be administered and an exhaled carbon monoxide (CO) will be measured to confirm smoking ($CO \geq 8$ ppm). A NicCheck using a urine sample will be performed (with a cut-off = 6 for those who otherwise qualify but for whom CO is < 8 ppm (e.g., they didn't smoke that morning, they came straight from work, etc.). Subjects who qualify and are interested in continuing will be invited to return to the baseline visit.

After eligibility is confirmed, subjects will begin receiving links daily via either text message or email (whichever they prefer) to a tobacco use survey that is to be completed on RedCap. On this survey subjects will report use of all tobacco and nicotine containing products used during the past day. These survey will continue until the end of the subject's participation in the study.

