9.0 Study Population

9.1 Inclusion Criteria: To be eligible subjects must:

- a) Be between the ages of 21 and 64
- b) Smoke (on average) at least 5 cigarettes per day over the past year
- c) Purchase exclusively menthol cigarettes
- d) Not currently motivated to quit smoking
- e) Able to receive daily text or email survey reminders and follow the link provided to complete the online RedCap surveys

9.2 Exclusion Criteria: Subjects will be excluded if they:

- a) Report a serious, unstable medical or psychiatric condition
- b) Have a history of substance abuse (other than nicotine) within 3 months of beginning the study
- c) Use any medications that might interfere with measures to be studied (for example, medications known to affect smoking)

- d) Have used any smoking cessation therapy during the past month
- e) Regularly use any form of tobacco other than cigarettes (> 9 times per month)
- f) Are pregnant or breast feeding or planning to become pregnant or breast feed during the study
- g) Currently participating in other clinical research studies

9.3 Screening: At the screening visit, subjects will complete a series of questionnaires including those that ask about medical history, smoking history, and motivation to quit smoking. All inclusion / exclusion will be based on self-report except for smoking status which will be confirmed via an exhaled carbon monoxide (CO) concentration of ≥ 8 ppm or a urinary nicotine test strip reading of 6. Non-pregnant status will be confirmed via a urine pregnancy test.

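### Does an ID check worded for age 18 leave the 21-to-64 inclusion limit unenforced?

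*Combined protocol and SAP*

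**What the plan says.** Three parts of the combined protocol and SAP bear on age.

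- **Section 9.1(a), inclusion criteria:** "Be between the ages of 21 and 64".
- **Section 9.3, screening:** "All inclusion / exclusion will be based on self-report except for smoking status", which is checked by exhaled carbon monoxide or a urine nicotine strip. One further objective check follows: "Non-pregnant status will be confirmed via a urine pregnancy test". Age is not listed among the confirmed items.
- **Section 21.4, in the consent section, on participants who are not yet adults:** "Individuals under the age of 18 will be excluded from the study", followed by "Subjects will be asked to present ID at the screening visit to confirm that they are at least 18 years of age".

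Section 5.2.1 sets out the order of events. "Initial eligibility will be assessed via a phone interview or online screening form housed on REDCap"; those who appear eligible then attend a screening visit, where consent is taken and eligibility is confirmed. That section does not mention ID.

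**The concern.** Read together, these sections suggest that the ID check was written against the wrong number. The inclusion criterion has two limits, 21 and 64. The only document check of age tests neither: it stops at 18 and says nothing about an upper bound. A coordinator who followed Section 21.4 literally, and nothing else, would be satisfied by ID from a person aged 18, 19, 20, or 65 and over. Section 9.3 does not close the gap, because it leaves age to self-report.

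If this were a real hole, people outside the target population could be randomised and given cigarettes, e-cigarettes and nicotine products by the study coordinator (Sections 4.1 and 4.2). There is some incentive to misreport, since Section 12.3 pays up to $190 and Section 5.1 lets unused credits be exchanged for money.

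**Working it through.** No formula applies; the check is a comparison of texts. The inputs are the limits in 9.1(a) (21 and 64) and the ID threshold in 21.4 (18). The difference at the lower end is 21 − 18 = 3 years of age, namely 18, 19 and 20.

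**Step 1. Apply both rules to each age band.**

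| Age | ID wording in 21.4 | Criterion 9.1(a) | Eligible on age under the plan |
|---|---|---|---|
| 17 or under | fails | fails | no |
| 18 to 20 | passes | fails | no |
| 21 to 64 | passes | meets | yes |
| 65 or over | passes | fails | no |

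The last column matches 9.1(a) in every row. Section 21.4 never makes an ineligible person eligible. Everyone under 18 is also under 21, so its exclusion is a subset of the one in 9.1(a). The two sections set different thresholds without contradicting each other.

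**Step 2. Ask what the ID check is for.** Its section concerns consent and its heading is confined to those under 18. Within that heading, 18 is the natural threshold and an upper limit has no place. No section says that the ID check is the means of verifying 9.1(a).

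**Step 3. Ask how 9.1(a) is applied.** Section 9.3 assigns age to self-report, as it does cigarettes per day, menthol-only purchasing, medication use and recent substance abuse. Section 5.2.1 then has eligibility confirmed at the screening visit. Under Section 21.4 the ID is shown at that same visit, so staff confirming eligibility have the birth date in front of them.

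**Step 4. Trace the route to a wrong enrolment.** Two things must both happen: the person misreports age, and staff who have seen the ID fail to apply 9.1(a) to it. The documents give no rate for either event.

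**Step 5. Look for an effect on the statistics.** Section 16.2 rests on 60 recruited, 10% dropout, 18 evaluable per group, a time-averaged effect size of 0.8, two-sided alpha of 0.05 and a within-subject autocorrelation of 0.6. The model in Section 16.1 has group, time, their interaction and random subject effects. None of these depends on how age is verified.

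**The case for a change.** The best argument for a change grants that Section 21.4 concerns minors. It says that a control tied to 18, with nothing tying it to 21 and 64, leaves the actual criterion resting on self-report in a paid study that hands out tobacco products. The background in Section 2.1 itself notes menthol's likely association with smoking initiation by youth and young adults. Sections 9.3 and 21.4 also differ on method: 9.3 describes only a breath or urine test for smoking and a pregnancy test as going beyond self-report, yet 21.4 asks for ID. Since the ID is already in hand, aligning the text would cost almost nothing.

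The facts in this stand. The thresholds differ, 9.3 omits the ID, and no other document check of age is described. The inference from them is weaker. Scoring the ID check against both limits of 9.1(a) holds it to a task the protocol never gave it, and the complaint about the upper limit is the least persuasive part. Moving age out of the self-reported criteria would also go beyond tidying the text: it would replace the chosen screening approach with a stricter one, and the documents show no benefit from doing so. A low cost of editing does not by itself make an edit necessary.

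**Conclusion.** The discrepancy is real but confined to wording. Followed as written, the plan excludes ages 18 to 20 and those over 64, because 9.1(a) governs entry and Section 21.4 only adds a check of adulthood. The effect on sample size, power and analysis is nil. The number of ineligible people who might enter cannot be estimated from the documents, and each would require both a misreport and a staff oversight.

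This rests on two assumptions: that staff confirming eligibility at the screening visit work from the criteria in Section 9, as Section 5.2.1 implies, and that they notice a birth date that conflicts with the reported age. Both are ordinary practice. If the protocol were being revised for another reason, a cross-reference from 21.4 to 9.1(a) would be a harmless editorial tidy-up, but the point does not warrant a change in its own right.
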